8.2 Number of Centres

This trial will be conducted at Cambridge University Hospitals NHS Foundation Trust.

8.3 Number of Subjects

A total of 30 evaluable patients are required.

Evaluable patients are those with all three tissue perfusion measurements collected by the surgeon at each of the three time points on both breasts during surgery.

8.4 Patient Study Duration

The study duration consists of up to 28 days eligibility requirement check period for patients, and if eligible, they will be registered. Registered patients will undergo surgery. The time between registration and surgery will vary between patients, and surgery will be scheduled in accordance with local procedures. Patients will be followed up post-surgery to observe their 30-day post-operative recovery period. As the study will follow the patient's standard of care visit schedule and the timing of these post-operative visits may differ between patients, it is expected that patients may be on study for up to 42 days post-surgery in order to capture

clinical information for the 30-day post-surgery period. Study completion will be defined as when the last patient registered has completed their last post-operative visit.

9 STUDY OBJECTIVES

9.1 Primary Objective

To determine if there is a difference in blood perfusion (Relative Value %) in the breast where the non-retractor technique is used during surgery versus the breast where the retractor technique is used in the same patient.

9.2 Secondary Objectives

To assess whether there are differences in the post-surgical complications, post-surgical recovery and post-surgical pain levels associated with the breast where the non-retractor technique is used during surgery versus the breast where the retractor technique is used in the same patient.

9.3 Exploratory Objectives

- 1. To evaluate the surgeon's experience of each different operative technique, retractors, and non-retractors.
- To assess the differences in overall operative times between the breast where the nonretractor technique is used during surgery, versus the breast where the retractor technique is used.

10 TRIAL ENDPOINTS

10.1 Primary Endpoint

The relative difference (%) in blood perfusion between each breast in the same patient. Blood perfusion will be measured at 3 time-points (T1: baseline, T2: mid-point, T3: end) during the mastectomy procedure. The relative difference is defined as the difference, D, of Blood perfusion at T2-T1. The t-test will be applied on the between-breast difference on D.

10.2 Secondary Endpoints

To compare the following post-surgical outcomes, as associated with the breast where the retractor technique is used during surgery versus the breast where the non-retractor technique is used, within the first 30 days post-surgery:

• Patient hospital re-admission, where applicable Perf-Act BreCon Protocol Version Number: 1.1 Version Date: 18/ Dec/ 2023

- Patient hospital stay duration, where applicable
- Patient re-operation required, where applicable
- Patient-reported post-surgery pain scores assessed at the following time points: 18 hours, follow-up week 1, week 2 and week 4-6
- Incidence, type and severity of surgery-related adverse events, where applicable

Comparison of patient's pre- and post-surgery outcomes as measured by Modules 7, 8, 9 and 14 of the BREAST-Q Recon version 2.0 questionnaire.

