8 STUDY DESIGN AND METHODS

8.1 Statement of Design

Patients (n=30) undergoing bilateral mastectomy with immediate breast construction (n=60 breasts) will be invited to take part in this prospective case-control, multi-centre study.

Consenting patients will complete a pre-operative questionnaire and then undergo surgery. In the same patient during the same operative episode, sequential tissue perfusion measurements will be taken as follows:

- First, in the right breast use the finger dissection non-retractor technique for as long as possible before reverting to metal retractors
- Secondly, in the left breast using retractors only throughout the entire procedure

The sequential measurements taken in each breast will allow for the comparison of tissue perfusion between the two different skin lift techniques.

Patients will be blinded to the technique used in each breast.

Following surgery, patients will be followed in order to observe the patient's 30-day postoperative recovery period.

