12.2.1 Surgery Procedure

The mastectomy with immediate reconstruction will be undertaken as per usual local procedures. Consented patients will undergo surgery and have sequential intra-operative fluorescence imaging assessments on each breast, whereby a fluorescent Indocyanine Green (ICG) dye will be injected intravenously and then detected using the Stryker's SPY-PHI handheld imager device to provide tissue perfusion measurements. The ICG dye will be administered intravenously as a bolus injection at the recommended dose of 0.1-0.3mg/kg body weight as per the manufacturer's guidelines for tissue perfusion diagnostics detailed in the ICG dye SmPC.

Right breast (Non-Retractor Technique)

The operating surgeon will first conduct the mastectomy procedure in the right breast using the non-retractor (finger dissection) technique to lift the breast tissue.

At the beginning of the mastectomy procedure, (defined as pre-incision on table and referred to as time TR1), and once confirmed that the fluorescent imager is ready to use, working and in hand, the surgeon will request that the ICG dye injection be administered to the patient. Once the dye is visualised, two tissue perfusion relative values (%) and the time in HH: MM (24hr format) will be taken and recorded. The first value will be the worst tissue perfusion relative value (%) observed in the 10x10cm area surrounding the incision, and the second value will be the best tissue perfusion relative value (%) observed anywhere in the breast.

The surgeon will then commence the mastectomy procedure and continue with the nonretractor (finger dissection) technique for as long as is comfortably possible and until finger fatigue prevents using this technique any longer. At this time point (referred to as TR2), the process of the ICG dye injection and two tissue perfusion measurements will be repeated as described for TR1.

After time point TR2 the surgeon will complete the mastectomy procedure using retractors to lift the breast tissue and the final ICG dye injection and two tissue perfusion measurements

will be completed at the end of the mastectomy procedure (defined as post-mastectomy before wound closure and referred to as time TR3).

In summary, the surgeon will request that the ICG dye be administered to the patient, after confirming the fluorescent imager is ready to use, working and in hand at the following three time points:

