12.3.1 Surgery-related Adverse Events

All adverse events considered by the Investigator to be surgery related will be recorded in the eCRF and classified using the NCI Common Terminology Criteria for Adverse Events (CTCAE) Version 5 criteria for preferred term and severity grading.

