13 COLLECTION OF CLINICAL DATA

No additional clinic visits or consultations are required for this study. Cancer patients will be followed up during their routine clinic visits/consultations, with study data collection time points approximating 1 week, 2 weeks, and 4-6 weeks post-surgery. Additional clinic assessments may be required per local practice, but study data collection will only occur at the approximate aforementioned time points.

The following clinical information will be collected at approximately week 1, week 2 and week 4-6 post-surgery:

- Re-admissions, where applicable (30-day Hospital re-admission rates, in line with HES)
- Patient hospital stay duration, where applicable
- Patient re-operation required, where applicable
- Patient-reported post-surgery pain scores for each breast

• Surgery-related adverse events, where applicable

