26 APPENDICES

26.1 Appendix 1: Schedule of Assessments

	Eligible to Register	Eligible to Pre Register surgery		Surgery			surgery	Follow-Up Approx. Week 1, Week 2 & Week 4-6
			T1	T2	Т3	1hr	18hrs (+/- 2hr)	
Informed consent	x							
Eligibility criteria assessment ¹	x							
BREAST-Q Version 2.0© Reconstruction Module questionnaire		x						x²
Demographics	x							
Worst Tissue perfusion relative value (%) in specified area for each breast			x	x	x			
Highest Tissue perfusion relative value (%) anywhere in the breast for each breast			x	x	x			
Surgeon questionnaire						x		
Patient reported pain scores (for each breast)							x	x
Surgery related adverse events								x
Patient re-admission, if applicable								x

Patient hospital stay duration, if applicable				x
Patient re-operation, if applicable				x

¹ To include review of the following: medical history, concomitant medication, most recent SoC pre-operative check blood results and pregnancy test results (where applicable)

² BREAST-Q post-operative questionnaire given at last follow up visit only (approximately 4-6 weeks post-surgery).

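### Hospital stay cannot be compared between breasts, and re-admission, re-operation and adverse events can be compared only if the protocol specifies how each event is attributed to a side

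*Protocol*

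**What the plan says.** Section 10.2 lists five outcomes over the first 30 days: re-admission, hospital stay, re-operation, patient-reported pain and surgery-related adverse events. All are to be compared "as associated with the breast where the retractor technique is used during surgery versus the breast where the non-retractor technique is used". The Synopsis and Section 17.2 repeat the list. The secondary objective in Section 9.2 uses the same unit for complications, recovery and pain, with each woman serving as her own comparison.

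On design, Section 8.1 places both techniques "In the same patient during the same operative episode": the right breast first with finger dissection, then the left with retractors.

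On data collection:
- Section 13 lists "Patient hospital stay duration, where applicable" and, for re-admission, "30-day Hospital re-admission rates, in line with HES". Re-operation is also worded as a patient item.
- Section 12.3.1 says "All adverse events considered by the Investigator to be surgery related will be recorded in the eCRF", classified by CTCAE version 5 term and grade.
- Appendix 1 has a row "Patient reported pain scores (for each breast"). Its rows for adverse events, re-admission, stay and re-operation name no breast.
- Section 15 refers the reader to a separate Case Report Form Guidelines document, which is not among the documents at hand.

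**The concern.** The comparison is promised at breast level, but most of the listed outcomes are described at patient level. A within-patient comparison needs two values per woman, one per breast, or an event that can be assigned to one breast. If the data are collected exactly as Sections 12.3.1, 13 and Appendix 1 describe them, only pain meets that condition.

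Complications are the clinical motive for the study: Section 7 argues from infection, re-admission, re-operation and implant loss. If side is not captured, the part of the secondary objective on complications and recovery cannot be answered between breasts, and pain is left on its own. A later analysis plan cannot restore a side that was never recorded.

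Reconstructing side afterwards would also be weak. The right breast always receives the finger technique first and the left always receives retractors only, so knowing the side means knowing the technique. Section 8.1 describes blinding for patients only.

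**Working it through.** **1. The plan's own figure.** Section 17.1 gives a difference of 10%, SD 25%, one-sided alpha 0.10 and power 80%.
- Normal approximation for a paired difference: n = ((1.2816 + 0.8416) × 25/10)² = 28.17, rounded up to 29.
- Exact noncentral t: power is 0.7997 at n=29 and 0.810 at n=30.

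The smallest n with at least 80% power is 30, so the stated size reproduces. It concerns perfusion only and does not depend on this point.

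**2. The five outcomes side by side.**

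| Outcome (10.2) | As described for collection | Breast named? | Between-breast comparison possible as written? |
|---|---|---|---|
| Pain | Section 13, Appendix 1: by breast | Yes | Yes |
| Hospital stay | Section 13: patient duration | No | No, by design |
| Re-admission | Section 13: 30-day rate in line with HES | No | Only with a cause attributed to a side |
| Re-operation | Section 13: patient item | No | Only if side is recorded |
| Surgery-related adverse events | Section 12.3.1: CTCAE term and grade | No | Only if side is recorded |

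**3. Hospital stay.** One operative episode gives one index admission, so 30 patients yield 30 durations. If a woman's stay L is assigned to both breasts, the paired difference is L − L = 0 for every patient whatever the techniques do. If it is not so assigned, the difference is undefined. Neither carries information about technique, and recording side would not help.

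**4. Re-admission, re-operation and adverse events.** Many of these have an identifiable side, such as a wound infection, skin necrosis, loss of an implant or a return to theatre for one breast. Others, such as a systemic or bilateral cause, do not. A paired comparison uses the women with an event on one side only; an event on both sides adds nothing to the difference. It therefore needs four states (right, left, both, not attributable) and a rule for choosing between them. No section gives either.

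**5. Rough scale, as illustration only.** Section 7 quotes 18% re-admission, 18% re-operation and 25% infection from a national audit. Assuming these apply per patient here:
- re-admission: 30 × 0.18 = 5.4;
- re-operation: 30 × 0.18 = 5.4;
- infection: 30 × 0.25 = 7.5.

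Section 7 gives no time window and does not say whether the unit is patient or breast. It also calls infection the leading cause of re-admission, so the counts overlap and must not be added.

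If m one-sided events all fell on the same breast, the exact two-sided paired p-value would be 2 × 0.5^m: 0.0625 for m=5 and 0.031 for m=6. With numbers this small, losing the side of even one or two events removes a large share of the information.

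**The case against.** The strongest reply is that silence is not a statement. A reader might infer that the three event outcomes are recorded without side, so that none of them can ever be compared between breasts. The documents do not support that.
- Appendix 1 also names no breast in its surgeon-questionnaire row, yet Appendix 2 scores that form separately for right and left. A missing label does not prove patient-level recording.
- The Case Report Form Guidelines are not shown and may already hold a laterality field.
- The wording of Section 10.2 presupposes some attribution to a breast, and the side of a re-operation or local wound event is usually an anatomical fact.

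This stands, and it limits the finding on those three outcomes to an unspecified side and rule. It does not remove the finding: the protocol labels pain by breast in the same list, and re-admission in particular needs a rule that an anatomical fact does not supply.

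A second reply is that hospital stay, qualified as where applicable and collected beside re-admissions, might mean days spent in a re-admission. That reading is possible. Those days would then need the same attribution to a side, and the index stay would still have no between-breast value.

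Third, nothing says that side would be assigned late from notes, and staff recording it at the time would know the technique too. Prompt recording therefore reduces discretion but does not blind the assessment.

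Finally, a reader might infer that the contrast is mislabelled, since "After time point TR2 the surgeon will complete the mastectomy procedure using retractors to lift the breast tissue" and 30-day outcomes therefore reflect fingers followed by retractors. But Sections 8.1 and 12.2.1 define the switch openly, and Section 10.3 makes the proportion of time before it an exploratory endpoint. Relabelling is a preference and not a correction.

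**Conclusion.** The point holds, with different strength by outcome. The between-breast comparison of index hospital stay is wrong as written: it has one value per patient, and no analysis plan or eCRF field can change that. For re-admission, re-operation and surgery-related adverse events, the comparison is conditional: it can be made only if each event is attributed to a side, and the protocol specifies no side and no rule. Of the five outcomes to be compared between breasts, one is impossible, three lack a stated basis and one (pain) is sound.

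The conclusion for stay rests on one operative episode and one index admission per woman, as Section 8.1 describes. The conclusion for the three event outcomes rests on the protocol text alone and would be met in part if the unseen eCRF already records side. The event counts above are illustrative and carry no weight in the conclusion.

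The weight is should-fix. These are secondary outcomes, and the primary endpoint and n=30 are unaffected.

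**What to change.** - **Sections 10.2 and 17.2 and the Synopsis:** take hospital stay out of the between-breast comparison and describe it per patient. State whether it means the index admission, re-admission days or both.
- **Sections 12.3.1 and 13 and Appendix 1:** for every surgery-related adverse event, re-operation and re-admission cause, record side as right, left, both or not attributable, at the time of the event. Add a short rule for assigning a re-admission to a breast.
- **Section 17.2:** compare attributable events as within-patient pairs, and describe non-attributable events per patient.

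The cost is one extra eCRF field on the event records, if it is not already there, and revised endpoint wording. No extra visits or patients are needed. Hospital stay is lost as a comparative endpoint, but it could not serve as one. The field has to be in place before events occur, because side may not be reliably recoverable afterwards.

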10.3 Exploratory Endpoints

- 1. Comparison of surgeon's self-reported scores of the following between retractor and nonretractor techniques:
 - Operative comfort
 - Operative difficulty/complexity
 - Operative visibility
 - Safety of technique
 - Physical demand of technique
- 2. Comparison of:
 - Overall operative time in breast where the non-retractor technique is used, versus the breast where the retractor technique is used, in the same patient.
 - Proportion of time before the retractor is used in the breast where non-retractor technique is employed.

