12.2.2 Post-Surgery

Following the conclusion of the surgery procedure, the surgeon will complete a short paper questionnaire for each breast surgery technique, refer to section 26.2, appendix 2: Surgeon Questionnaire.

The study team will record the patient-reported pain scores in both breasts at 18 hours (+/- 2 hours) post-surgery.

Patient will be asked to complete Modules 7, 9 and 14 of the BREAST-Q Version 2.0© Reconstruction questionnaire at their last follow up visit.

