17.2 Analysis of Endpoints

- **Primary Outcome** – The relative difference (%) in blood perfusion between each breast in the same patient. Blood perfusion will be measured at 3 time-points (T1: baseline, T2: midpoint, T3: end). The relative difference is defined as the difference, D, of Blood perfusion at T2-T1. The t-test will be applied on the between-breast difference on D.

- Secondary Outcomes -

To compare the following post-surgical outcomes, as associated with the breast where the retractor technique is used during surgery, versus the breast where the non-retractor technique is used, within the first 30 days post-surgery:

- o Patient hospital re-admission, where applicable
- o Patient hospital stay duration, where applicable
- o Patient re-operation required, where applicable
- Patient-reported post-surgery pain scores assessed at the following time points: 18hrs, follow-up week 1, week 2 and week 4-6
- o Incidence, type and severity of surgery related adverse events, where applicable

Comparison of patients' pre- and post-surgery outcomes as measured by Modules 7, 8, 9 and 14 of the BREAST-Q Recon version 2.0 questionnaire.

- Exploratory Outcomes -

1. Comparison of surgeons self-reported scores of the following between retractor and nonretractor technique:

- o Operative comfort
- o Operative difficulty/complexity
- o Operative visibility
- o Safety of technique
- o Physical demand of technique
- 2. Comparison of:

- Overall operative time in breast where the non-retractor technique is used, versus the breast where the retractor technique is used, in the same patient.
- Proportion of time before the retractor is used in the breast where non-retractor technique is employed.

The primary endpoint will be measured through sequential intra-operative fluorescence imaging assessments on each breast during the surgery, whereby a fluorescent Indocyanine Green (ICG) dye will be injected intravenously into the patient at three different time points: at the beginning of the surgery, halfway through the surgery, and at the end of the mastectomy procedure. The dye will be detected using the handheld Stryker's SPY-PHI imager device to provide tissue perfusion measurements.

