26.2 Appendix 2: Surgeon Questionnaire

Question	Score for the right breast (Non- retractor technique)	Score for the left breast (Retractor technique)
1. How physically fatiguing was the procedure? (0–10 scale; 0—not at all demanding; 10— extremely demanding) (17)		
2. How complex was the procedure? (0–10 scale; 0—not at all complex; 10—extremely complex) (18)		
3. What was the degree of difficulty of the operation? (0-10 scale; 0-not at all difficult; 10-extremely difficult)(18)		
4. Compared to other mastectomies of this type, how difficult was this operation? (0–10 scale; 0– not at all difficult; 10—extremely difficult) (19)		
5. How difficult was visualization during the operation? (0–10 scale; 0—not at all difficult; 10— extremely difficult) (19)		
6. How fatigued were you at the end of the operation? (0-10 scale; 0-not at all fatigued; 10-extremely fatigued) (18)		
 7. What is your degree of satisfaction with the technique used to complete the surgery? (0–10 scale; 0—not at all satisfied; 10—extremely satisfied) (Original to this study) 		

8 . Rate your perception of the safety of each soft tissue lift technique to the soft tissue around the	
incision (0-10 scale; 0-not at all safe; 10-extremely safe) (Original to this study)

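### Operative comfort is a listed surgeon score, but no item in the Appendix 2 questionnaire asks about it

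*Protocol*

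**What the plan says.** Exploratory objective 1 (section 9.3) concerns the surgeon's experience of each technique. Section 10.3 turns this into an endpoint: "Comparison of surgeon's self-reported scores of the following between retractor and nonretractor techniques". Five domains follow: comfort, difficulty or complexity, visibility, safety and physical demand. The synopsis (section 5) and section 17.2 carry the same list. In all three places "Operative comfort" comes first and "Physical demand of technique" is a separate entry.

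Section 12.2.2 names the instrument: after surgery "the surgeon will complete a short paper questionnaire for each breast surgery technique". The schedule in Appendix 1 shows one surgeon assessment, at one hour after surgery. Appendix 2 prints the form: eight items, each scored 0 to 10, with one column for the right breast (non-retractor) and one for the left (retractor). No other part of the protocol collects a score from the surgeon.

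**The concern.** The endpoint list and the data collection form should agree, because a score that is not asked for cannot be compared. The list promises a comfort score and the form has no comfort question. The protocol also separates comfort from physical demand, so a reader cannot simply assume that the item on physical fatigue was meant to cover both.

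What is at stake is modest: one of the five measures that make up the surgeon-experience endpoint. Timing does matter. The form is filled in about an hour after surgery, and a question left out then cannot be recovered reliably later.

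**Working it through.** The protocol gives no figure to reproduce here. The check is a match between the two lists.

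**Inputs.** Five domains from section 10.3 (same list in sections 5 and 17.2), and eight items from Appendix 2.

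**Match by domain**

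| Domain in section 10.3 | Item(s) in Appendix 2 |
|---|---|
| Difficulty/complexity | 2 ("How complex was the procedure"), 3 (degree of difficulty), 4 (difficulty relative to similar mastectomies) |
| Visibility | 5 (difficulty of visualisation) |
| Safety | 8 (perceived safety of the lift technique) |
| Physical demand | 1 ("How physically fatiguing was the procedure", with end-points worded in terms of demand) |
| Comfort | none |

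**Count.** Four of five domains have a direct item and one of five has none. The direct matches use items 1, 2, 3, 4, 5 and 8, which is six of eight. Items 6 and 7 are left over (8 − 6 = 2).

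**Could a left-over item be the comfort score?**

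- Item 6 asks how fatigued the surgeon was when the operation ended. Fatigue is closer to physical demand, which is already a separate domain. The design also makes item 6 an indirect guide to comfort with the finger technique: under sections 8.1 and 12.2.1 the right breast is operated on first and finished with retractors, so fatigue at the end reflects the retractor phase as well.
- Item 7 asks "What is your degree of satisfaction with the technique used to complete the surgery". A surgeon may be satisfied with a technique that was uncomfortable to perform, or the reverse. The protocol does not link the item to comfort.

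The two candidates also differ in direction: a high score is unfavourable on item 6 and favourable on item 7. They are not interchangeable readings of one construct.

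**The case against.** The strongest reply is that section 10.3 lists domains rather than item titles, and that the other matches are loose too: physical demand is scored by an item on fatigue, and visibility by an item on visualisation. Once the direct matches are made, comfort is the only domain left and items 6 and 7 are the only items left. Section 12.2.1 itself puts comfort next to finger fatigue when it describes how long finger dissection continues. Item 1 rates the procedure while item 6 rates the surgeon's own state, which would give a reason for two domains. Assigning items to domains is also ordinary SAP content, and the SAP is not shown.

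Much of this stands, and it rules out several stronger readings that a reader might infer:

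- **That the endpoint cannot be produced at all.** A proxy could be named, and the wording of section 12.2.1 makes fatigue a plausible one.
- **That any proxy would be chosen after the scores are seen.** A SAP may fix the choice in advance, and its absence from the material at hand shows nothing either way.
- **That comfort is central to the study's rationale.** Section 7 is about tissue trauma, perfusion and fingers tiring. The mention of comfort is a procedural instruction in section 12.2.1.
- **That item 7 is an error because no listed endpoint uses it.** It serves the broader objective on surgeon experience.
- **That the wording of item 1 undermines the physical-demand score.** The question speaks of fatigue and its end-points of demand, but this is a minor slip, since the same item is scored for both breasts.

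The reply does not remove the mismatch. A SAP can assign a proxy, but it cannot supply an answer to a question the printed form does not ask. The looser matches elsewhere still concern recognisably the same construct, whereas for comfort the link has to be inferred.

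**Conclusion.** The point holds as a mismatch inside the protocol: one of five surgeon scores named in sections 5, 10.3 and 17.2 has no direct item among the eight in Appendix 2. Fatigue at the end of the operation and satisfaction are at best proxies, and the protocol designates neither.

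This rests on two readings. The first is that Appendix 2 is the complete and only surgeon instrument, as section 12.2.2 and the schedule indicate. The second is that comfort differs from physical demand, as the separate listing implies.

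The importance is low. The gap touches a single exploratory endpoint and leaves the primary analysis and the planned 30 evaluable patients unaffected. It is worth correcting because the repair is small and is best made before the forms are in use.

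**What to change.** Preferred: add one operative-comfort item, scored 0–10 for each breast with labelled end-points, to Appendix 2, and add the matching fields to the eCRF. The three endpoint lists can then stay as they are.

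If the questionnaire is to remain unchanged, remove operative comfort from sections 5, 10.3 and 17.2, or rename it to the construct actually asked. Renaming to satisfaction (item 7), for example, would be a change of endpoint and should be presented as one, not as a way of measuring comfort.

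The first option costs one questionnaire line, two scores per patient and the eCRF update. The second costs a wording change in three places. Either needs a short protocol amendment. Surgeries scored before a new item is introduced would have no comfort score.
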